#### 4. STUDY DESIGN

# 4.1. Overall Design

This is a Phase 1 study in up to a maximum of 48 healthy adult participants (36 on active treatment, 12 on PBO). The study will consist of 2 SAD (Cohorts 1 and 2) and 4 MAD cohorts (Cohorts 3 to 6). Cohort 6 will enroll Japanese participants. Eight participants will be randomly assigned in a 6:2 ratio in each of the 6 cohorts to receive either single or multiple SC doses of ALXN1830 (n = 6 per cohort) or single or multiple doses of PBO (n = 2 per cohort). The planned study duration is approximately 124 days for Cohorts 1 and 2: up to 60 days for screening and approximately 64 days for dosing and follow-up; 201 days for Cohort 3: up to 60 days for screening and approximately 141 days for dosing and follow-up; and 148 days for Cohorts 4 to 6: 60 days for screening and approximately 88 days for dosing and follow-up. Participants will be admitted to an inpatient facility during the dosing and follow-up period as shown in Section 1.3.

Initially, the first 4 participants randomized to each cohort will be dosed with 3 participants on active treatment and 1 participant on PBO. The dosing will be staggered, with an interval of at least 3 days for the SAD cohorts and at least 7 days for the MAD cohorts, before dosing the rest of the participants in the cohort. The shorter interval of staggered dosing for the SAD cohorts compared to the MAD cohorts is considered appropriate as the expected PK exposure of the ALXN1830 SC doses will be a fraction of that of the IV dose demonstrated to be safe and well tolerated in previous IV studies. The reduction of IgG after a single SC dose will be similar to the observed IgG reduction in previous IV studies; and in general, there will be low risk of immunogenicity and IRRs after a single dose. See Section 4.3 for details regarding expected PK exposures and IgG reduction. All participants will be observed during the drug administration and for 2 hours after dosing for safety and participants will be encouraged to report any discomfort immediately, especially within 24 hours post dosing. At no time will more than 4 participants per cohort be dosed on a given day.

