# 7.2.2. Safety Stopping Rules (Individual, Cohort and Study Level Stopping Rules) Individual Level:

- Study drug will be discontinued immediately (if applicable) and permanently if any of the following occurs:
  - Development of a 'serious' adverse reaction (AR), or 'severe' (≥ Grade 3) AR.
  - Development of a 'serious' adverse reaction (AR), or 'severe' (≥ Grade 3) IRR.
- If a moderate Grade 2 AR is observed, study drug administration may be continued, delayed, or discontinued in accordance with Investigator's clinical judgment and in consultation with Alexion.

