#### **Cohort and Study Level:**

- A cohort and other cohort with a dose at an equal or higher level will be stopped or not initiated if any of the following occurs:
  - 2 participants on study drug in the cohort experience a moderate (Grade 2) AR
     that does not improve by 14 days after treatment
  - $\geq$  2 participants on study drug in the cohort experience an IRR as described earlier (see individual level)
- Study will be discontinued (all dosing [lower, equal, or higher doses]) and continuation of the cohort or study will require a substantial amendment, if any of the following occurs:
  - Two participants on study drug in any cohort experience a severe (Grade 3) AR
  - One participant on study drug in any cohort experiences a serious AR

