Infusion-related reaction	Mild transient reaction; infusion interruption not indicated; intervention not indicated	Therapy or infusion interruption indicated but responds promptly to symptomatic treatment (eg, antihistamines, non-steroidal anti-inflammatory drugs [NSAIDs], narcotics, IV fluids): prophylactic medications indicated for ≤ 24 hours	Prolonged (eg, not rapidly responsive to symptomatic medication and/or brief interruption of infusion); recurrence of symptoms following initial improvement, hospitalization indicated for clinical sequelae	Life-threatening consequences; urgent intervention required	Death	
Allergic reaction	Transient flushing or rash, drug fever < 38.0°C. Intervention not indicated	Therapy or infusion interruption indicated but responds promptly to symptomatic treatment (eg, antihistamines, NSAIDs, narcotics, IV fluids): prophylactic medications indicated for ≤ 24 hours	Prolonged (eg, not rapidly responsive to symptomatic medication and/or brief interruption of infusion); recurrence of symptoms following initial improvement, hospitalization indicated for clinical sequelae (eg, renal impairment, pulmonary infiltrates)	Life-threatening consequences; urgent intervention required	Death	
Anaphylaxis	-	_	Symptomatic bronchospasm, with or without urticarial; parenteral intervention indicated; allergy-related edema/angioedema; hypotension	Life-threatening consequences; urgent intervention required	Death	
Cytokine release syndrome	Mild reaction; infusion interruption not indicated; intervention not indicated	Therapy or infusion interruption indicated but responds promptly to symptomatic treatment (eg, antihistamines, NSAIDs, narcotics, IV fluids): prophylactic medications indicated for ≤ 24 hours	Prolonged (eg, not rapidly responsive to symptomatic medication and/or brief interruption of infusion); recurrence of symptoms following initial improvement, hospitalization indicated for clinical sequelae (eg, renal impairment, pulmonary infiltrates)	Life-threatening consequences; pressor or ventilator support indicated	Death	

Abstracted from NCI CTCAE Version 5.0.

Abbreviations: IV = intravenous; NSAIDs = nonsteroidal anti-inflammatory drugs

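### Repeated resolving Grade 2 infusion-related reactions trigger no automatic cohort action in Protocol 7.2.2; add a pause for Safety Review Committee review and keep the existing Grade 3+ stop

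*Protocol*

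**What the plan says.** Protocol Section 7.2.2 sets rules at three levels.

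- **Individual.** Study drug is permanently discontinued on "Development of a 'serious' adverse reaction (AR), or 'severe' (≥ Grade 3) IRR". After a Grade 2 adverse reaction (AR), dosing "may be continued, delayed, or discontinued in accordance with Investigator's clinical judgment and in consultation with Alexion".
- **Cohort.** The cohort, and any cohort at an equal or higher dose, is stopped or not started in either of two cases. One is two participants with a Grade 2 AR "that does not improve by 14 days after treatment". The other is two or more "participants on study drug in the cohort experience an IRR as described earlier (see individual level".
- **Study.** All dosing stops, and resuming needs a substantial amendment, if "Two participants on study drug in any cohort experience a severe (Grade 3) AR" or "One participant on study drug in any cohort experiences a serious AR".

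Table 20 (Section 10.4) describes a Grade 2 IRR as "Therapy or infusion interruption indicated but responds promptly to symptomatic treatment". A prolonged reaction, or one that returns after first improving, is Grade 3.

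Section 4.1 says "there will be low risk of immunogenicity and IRRs after a single dose". Sections 2.1 and 2.3.3 report that IRRs with multiple 20 mg/kg IV doses were mild or moderate and all resolved. They also ended treatment for those affected and led to the study being paused.

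**The concern.** Section 2.3.3 treats the earlier IRRs as a reason for risk mitigation and lists stopping rules among the measures. The stopping rules are nevertheless set at a severity those reactions did not reach. Mild-to-moderate, resolving IRRs in several participants of one weekly-dosing cohort would not, by rule, lead anyone to pause and look at the cohort as a whole. At stake is continued weekly dosing of healthy volunteers, with the decision resting on judgement and no count that obliges a review.

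**Working it through.** The documents give no operating characteristics for the stopping rules, so there is no figure to reproduce. AR is read here as an adverse event judged related to study drug.

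**1. Is the cohort IRR bullet contained in the study-level stop?** Take two participants whose IRRs meet the individual-level criterion and count as ARs. If either IRR is serious, the one-serious-AR rule is met. If neither is, both are Grade 3 and the two-Grade-3 rule is met.

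Enumeration agrees. Give each of 6 active participants one of five worst-IRR states: none, Grade 1 resolved, Grade 2 resolved, Grade 3 non-serious, or serious/Grade 4+.
- Profiles: 5^6 = 15,625.
- Fewer than two participants in the top two states: 3^6 + 6×2×3^5 = 729 + 2,916 = 3,645.
- Cohort rule met: 15,625 − 3,645 = 11,980. All of these also meet a study-level rule.

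If some IRRs are judged not to be ARs, the cohort rule can act alone.

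**2. Does the Grade 2 AR bullet catch Grade 2 IRRs?** It needs no improvement by 14 days. Table 20 makes prompt response part of Grade 2 and moves prolonged or recurrent reactions to Grade 3, so the conditions exclude each other. A lingering symptom could be recorded separately as a Grade 2 AR, but a resolving IRR does not qualify. With weekly dosing, a 14-day wait also spans up to two further doses. Six of 6 active participants with a resolved, non-serious Grade 2 IRR therefore meet neither the cohort nor the study rule.

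**3. Where is the gap?** Inputs: Table 15 and the schedules of activities.
- *Cohorts 4 and 5* dose on Days 1, 8, 15 and 22. At its 7-day minimum, the sub-cohort review covers one dose in 4 participants (3 active). The SRC gate for the next dose level uses data through Day 22, the day of the last dose. Doses 2 to 4 fall between these points.
- *Cohort 3* doses weekly on Days 1 to 78 (12 doses). Assume a 7-day stagger and no SRC delay, and count in first-sub-cohort days. Six participants with Day 22 data require the second sub-cohort, so the Cohort 4 gate is at 22 + 7 = Day 29. The Cohort 5 gate is at 29 + 7 + 21 = Day 57. Doses up to the first gate, between the gates and after the second are 5, 4 and 3 in the first sub-cohort, and 4, 4 and 4 in the second.

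**4. What would a pause at 2 or more of 8 dosed participants do?** All rates are assumed. The documents give a count of 6 earlier IRRs (Table 13) but no number exposed at 20 mg/kg IV.

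False pause, all 8 at background rate p: q = 1 − (1−p)^8 − 8p(1−p)^7. At least one in six cohorts: 1 − (1−q)^6.

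| p | q per cohort | any of six cohorts |
|---|---|---|
| 2% | 1.0% | 6% |
| 5% | 5.7% | 30% |
| 10% | 18.7% | 71% |

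For example, at 5%: 1 − 0.6634 − 0.2793 = 0.0572.

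True signal, 6 active at rate p and none on saline: 1 − (1−p)^6 − 6p(1−p)^5. The last column adds 2 saline participants at 5%.

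| p on ALXN1830 | saline 0% | saline 5% |
|---|---|---|
| 20% | 34% | 38% |
| 30% | 58% | 61% |
| 50% | 89% | 90% |

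Under the present text the probability of an automatic action for non-serious, resolving Grade 2 IRRs is zero at every rate.

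**The case against.** The best reply is that the protocol relies on close oversight, and there is a good deal of it:
- sponsor notification within 24 hours of an infusion reaction that interrupts or ends treatment, while Grade 1 and 2 reactions should themselves prompt a temporary stop (10.4);
- sponsor consultation on Grade 2 ARs (7.2.2);
- power for the Investigator or SRC to modify dosing, and for the SRC to recommend suspension (6.6);
- immediate discussion of immediate safety concerns (Section 8);
- an unblinded medical monitor (2.3.3, 10.7);
- SRC approval before each escalation (Table 15), and SRC review of Cohort 5 through Day 36 before Cohort 6 (4.3).

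The SRC charter, which is not among the documents, may add an ad hoc trigger. The earlier pause is also consistent with judgement having worked; the documents do not say that a numerical rule caused it. The risk may be lower now. Impurities may have confounded the earlier IRRs, manufacturing has changed, and exposure at 1500 mg SC is predicted at one-fifth to one-eighth of that at 30 mg/kg IV.

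All of that stands, and it rules out several stronger readings that a reader might infer. The scheduled reviews do not mostly miss the relevant doses: the Day 22 gates take in doses 1 to 3 and the day of dose 4, and Cohort 3 can have two gates during its dosing. Higher doses do not start by default. The cohort bullet is not empty, because it needs no causality judgement. The earlier pause does not prove that a count-based trigger is needed.

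What the reply does not supply is an automatic cohort action. Each listed safeguard is a notification, a discretionary power or a review at a scheduled point.

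The proposed threshold also discriminates only modestly: 34% at a true 20% rate on active, against 18.7% at a 10% background. That supports a pause for review and would not support a stop.

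**Conclusion.** The point holds in a limited form. For drug-related reactions the cohort IRR bullet adds nothing to the study-level stop. Repeated non-serious, resolving Grade 2 IRRs, including those ending treatment, set off no automatic cohort action, even at 6 of 6 active participants. The exposed period is doses 2 to 4 within Cohorts 4 and 5, and in Cohort 3 the 4 doses between the SRC gates and 3 to 4 after them on the fastest schedule.

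This rests on reading the cross-reference literally, on Table 20 governing IRR grades, and on the protocol text alone. If the sponsor meant any IRR, the cross-reference needs correcting. It would go too far to conclude that such reactions would pass unnoticed or that the study is unsafe; the oversight described above argues against both. The change is an inexpensive improvement to participant protection.

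SAP Section 4.1 records early termination with no Cohort 6 participants. It gives no reason, and none connected with IRRs should be inferred.

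**What to change.** Keep the existing Grade 3+ cohort stop and add a bullet to 7.2.2:

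> If 2 or more dosed participants in a cohort have an IRR leading to permanent discontinuation, or a Grade 2 or higher IRR (excluding isolated headache), further dosing in that cohort and at equal or higher doses pauses until the SRC has reviewed and documented a decision.

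The bullet should be added and not substituted. Replacing the present one would turn a stop that applies whatever the causality into a pause, for Grade 3+ IRRs judged unrelated. Counting everyone dosed avoids unblinding. Isolated headache is excluded because Section 10.4 lists it as an infusion-reaction symptom and Section 2.3.3 reports it in 100% at multiple 20 mg/kg IV doses. If the SRC charter already holds such a trigger, citing it in 7.2.2 is enough.

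The cost is one bullet and matching charter text. Each pause then means an unscheduled SRC meeting and possibly a delayed weekly dose, which would disturb that week's trough PK. The headache exclusion is meant to keep the background rate, and so the false-pause probability, at the low end of the range shown.

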## 7.3. Participant Discontinuation/Withdrawal from the Study

- All efforts should be made to ensure participants are willing to comply with study
  participation prior to conducting the screening procedures. The study staff should
  notify Alexion and their site monitor of all study withdrawals as soon as possible. The
  reason for participant discontinuation must be recorded in the source documents and
  CRF.
- A participant may withdraw from the study at any time at his/her own request or may be withdrawn at any time at the discretion of the Investigator for safety, behavioral, compliance, or administrative reasons. This is expected to be uncommon.
- At the time of discontinuing from the study, if possible, an early termination visit should be conducted, as shown in the SoA (Section 1.3). See SoA for data to be collected at the time of study discontinuation and follow-up and for any further evaluations that need to be completed.
- The participant will be permanently discontinued both from the study drug and from the study at that time.
- If the participant withdraws consent for disclosure of future information, Alexion may retain and continue to use any data collected before such a withdrawal of consent.
- If a participant withdraws from the study, he/she may request destruction of any samples taken and not tested, and the Investigator must document this in the site study records.

Not all participants who withdraw will be replaced. At Alexion's discretion, and after consultation with the SRC, additional participants may be enrolled as replacement participants only if a participant discontinues within 3 weeks of the last dose for reasons other than drug-related AEs.

# 7.4. Lost to Follow-up

A participant will be considered lost to follow-up if he or she repeatedly fails to return for scheduled visits and is unable to be contacted by the study site.

The following actions must be taken if a participant fails to return to the clinic for a required study visit:

- The site must attempt to contact the participant and reschedule the missed visit as soon as possible and counsel the participant on the importance of maintaining the assigned visit schedule and ascertain whether the participant wishes to and/or should continue in the study.
- Before a participant is deemed lost to follow-up, the Investigator must make every
  effort to regain contact with the participant (where possible, 3 telephone calls and, if
  necessary, a certified letter to the participant's last known mailing address or local
  equivalent methods). These contact attempts should be documented in the
  participant's medical record.

• Should the participant continue to be unreachable, he/she will be considered to have withdrawn from the study.

Discontinuation of specific sites or of the study is handled as part of Section 10.1.9 Study and Site Start and Closure.

The Investigator, competent authority, or Sponsor may terminate the study for reasonable cause. Conditions that warrant termination of the study include, but are not limited to, the following:

- Discovery of an unexpected, serious, or unacceptable risk to participants enrolled in the study.
- Decision on the part of Alexion to suspend or discontinue testing, evaluation, or development of the study drug.
- Failure of the Investigator to comply with the approved protocol, pertinent guidelines, and/or regulations.
- Submission of knowingly false information from the Investigator to Alexion and/or regulatory authorities.

#### 8. STUDY ASSESSMENTS AND PROCEDURES

- Study procedures and their timing are summarized in the SoA (Section 1.3). Protocol waivers or exemptions are not allowed.
- Immediate safety concerns should be discussed with Alexion immediately upon occurrence or awareness to determine if the participant should continue or discontinue study drug.
- Adherence to the study design requirements, including those specified in the SoA, is essential and required for study conduct.
- All screening evaluations must be completed and reviewed to confirm that potential
  participants meet all eligibility criteria. The Investigator will maintain a screening log
  to record details of all participants screened and to confirm eligibility or record
  reasons for screening failure, as applicable.
- Procedures conducted as part of the participant's routine clinical management (eg, blood count) and obtained before signing of the ICF may be utilized for screening or baseline purposes provided the procedures met the protocol-specified criteria and were performed within the time frame defined in the SoA.

## 8.1. Efficacy Assessments

No efficacy assessments will be obtained during the study.

## 8.2. Safety Assessments

Planned time points for all safety assessments are provided in the SoA (Section 1.3).

#### **8.2.1.** Physical Examinations

A full physical examination will be performed at Screening. A symptom-driven physical examination will be performed predose and at the EOS visit and may be performed at other times, at the Investigator's discretion.

Each examination will include the following assessments: general appearance; skin; head, ears, eyes, nose, and throat; neck; lymph nodes; chest; heart; abdominal cavity; limbs; central nervous system; and musculoskeletal system.

Height and BMI will be recorded at Screening. Weight will also be recorded predose.

#### 8.2.2. Vital Signs

• Vital signs will be taken after the participant has been resting in the supine or semi recumbent position for at least 5 minutes and will include temperature (°C); tympanic or oral), respiratory rate, and pulse oxymetry. The timing of vital sign measurements is described in the SoA (Section 1.3). Out of range BP or pulse measurements will be repeated at the Investigator's discretion. Confirmed, clinically significant vital sign measurements will be recorded as AEs.

- Blood pressure and pulse measurements will be assessed in a semi-supine position
  with a completely automated device. Manual techniques will be used only if an
  automated device is not available.
- Blood pressure and pulse measurements should be preceded by at least 5 minutes of rest for the participant in a quiet setting without distractions (eg, television, cell phones). Ideally, the same arm for each participant should be used for measurements.

#### 8.2.3. Electrocardiograms

12-lead electrocardiogram (ECG) will be conducted as outlined in the SoA (see Section 1.3) to obtain heart rate, PR, QRS, QT, and QTc intervals after participant has been in the supine position for at least 5 minutes.

The subjects will avoid postural changes, and clinical staff will ensure that subjects are awake during the ECG recording.

At each time point, the ECG will be recorded in triplicate, to reduce variance and improve the precision of measurement. The triplicates will be performed at approximately 1-minute intervals. Each ECG recording (trace) will last 10 seconds. Repeat ECGs will be performed until at least three 10-second ECG records per scheduled time point meet the quality criteria.

#### 8.2.4. Clinical Safety Laboratory Assessments

- See Section 10.2 for the list of clinical laboratory tests to be performed and to the SoA (Section 1.3) for the timing and frequency.
- The Investigator must review the laboratory report, document this review, and record any clinically relevant changes occurring during the study in the AE section of the case report form (CRF). The laboratory reports must be filed with the source documents
- All laboratory tests with values considered clinically significantly abnormal during participation in the study or within 5 half-lives after the last dose of study drug should be repeated until the values return to normal or baseline or are no longer considered clinically significant by the Investigator or Medical Monitor.
  - If such values do not return to normal/baseline within a period of time judged reasonable by the Investigator, the etiology should be identified, and Alexion notified.
  - All protocol required- laboratory assessments, as defined in Section 10.2, must be conducted in accordance with the laboratory manual and the SoA.
  - If laboratory values from non-protocol specified laboratory assessments
    performed at the institution's local laboratory require a change in participant
    management or are considered clinically significant by the Investigator (eg, SAE
    or AE or dose modification), then the results must be recorded in the CRF.

#### 8.2.5. Virus Serology

Blood samples collected at Screening will be analyzed for HIV-1, HIV-2, HBsAg, hepatitis B core antibody, and hepatitis C virus antibody titers.

#### 8.2.6. Vaccination

Participants will be adequately vaccinated as described in Section 6.5.3 and Section 5.1.

## 8.2.7. Drug and Alcohol Screen

A urine sample for drug screen will be analyzed for the substances listed in Section 10.2. Timing of urine drug and alcohol breath tests is specified in the SoA (Section 1.3).

